## 1.2. STUDY OVERVIEW

### **1.2.1. The first goal of the SPRING protocol is to test the safety and the activity of the selected tri-therapy in patients with metastatic NSCLC patients in first therapeutic line for the phase 2 portion of the trial (for the phase 1 patients with a maximum of 2 prior lines will be accepted).**

The trial will start with a Phase 1 safety study to establish the dose of each of the three agents. This part of the study will require about 30 patients treated (~40 patients enrolled). The Phase 1 will be followed by a first extension Phase 2 to test efficacy on up to 100 patients who will all receive the tri-therapy (100 patients treated/ ~120 patients enrolled (~20 patients screen failures)). All patients will have the necessary biopsies performed to ensure that adequate biopsy material is available before starting treatment. For ethical reasons, patients whose biopsies fail to produce interpretable data will still be treated with the tri-therapy. Pending clinical activity, the study may be extended by an additional 100 patients treated (total = 200 patients on the phase 2 portion) in order to firm up the initial efficacy assessment and identify the potential subgroups of patients with clinically meaningful efficacy.

Patients with specific documented oncogenic aberrations (EGFR mutations, ALK translocations, ROS1 if available and MET exon 14 skipping mutation if available) will be excluded from the trial. The study cohort will aim to include patients who are not generally treated with specific targeted therapeutics. Patients will be included in the study regardless of their PD1 or PD-L1 expression status. In the case of patients already treated on SPRING protocol who are later determined to have EGFR mutation or ALK translocation or ROS1 or MET exon 14 skipping mutations after SIMS analyses, amenable to treatment with an approved therapy, they will be given the option to continue investigational treatment in the SPRING trial after obtaining appropriate re-consent or discontinue treatment.

Early futility stopping rules will be applied in the phase 2 study should the tri-therapy have less than the expected efficacy to guard against patients being enrolled in ineffective treatment.

We estimate that overall 85% of the patients treated in the trial will have a profile that is matched to at least one out of the three drugs: 10% matched with three drugs, 36% matched with two drugs and 39% matched with one drug.

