#### Criteria of success:

- We will document best response in all patients. Patients shall be followed for at least six months on treatment (providing their tumors do not progress earlier) in order to document best response: The trial will be considered as meeting its primary endpoint if a 6-month response rate (% of patients achieving RECIST 1.1 complete or partial response within 6 months of treatment start) of 50% is achieved for patients who are fully matched according to the SIMS retrospective analysis and is superior to the partially matched arms. With a type I error of 10% and a power of 94%, 20 patients fully matched will be enough to demonstrate the usefulness of the approach assuming a null response rate of 20% based on the one-sided Fisher's exact test. This would require a cohort of 200 patients treated. Nevertheless, we intend to treat an initial cohort of 100 patients as an exploratory observational study. Pending clinical activity, the study could be extended to an additional 100 patients treated in order to attain sufficient statistical power to support the validity of the approach.
- SIMS will show clinical utility:
  - If the proportion of patients fully matched to the combination versus partially matched estimated using SIMS (20/80) is similar to the observed proportion in the SPRING cohort (maximum coefficient variability allowed 20%),
  - If fully matched patients show significantly better clinical outcomes than the partially matched ones and the fully or partially matched ones show significantly better clinical outcomes than the non-matched ones.

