## 7.2. PHASE 2 EFFICACY EVALUATION

The Phase 2 study will be conducted in two parts. In the first part of the Phase 2 study, we expect to enroll approximately 120 patients in order to obtain 100 patients eligible for the study treatment. Futility early stopping rule will be implemented to ensure that the treatment has met the minimum efficacy requirements. If not meeting the minimum efficacy requirement, the trial will be stopped early. If the trial is not stopped early after the first 100 patients, the study could be extended, (with an amendment) to the second part of the Phase 2 study in order to reach a total of 200 patients treated.

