### 7.2.1. Statistical analysis of the primary efficacy end point

The primary efficacy evaluation for measuring a clinical meaningful improvement is defined as demonstrating an improvement of the primary efficacy endpoint of 6-month objective response rate from 20% (under the null hypothesis) to 50% (under the alternative hypothesis) in the fully matched arm. With 5% one-sided type I error, we need to treat 20 patients to demonstrate the usefulness of the tri-therapy approach to achieve and 86% power based on the exact binomial test. With an expected 10% of patients who will be fully matched, we need to enroll 200 patients in the study. All inevaluable patients will be replaced. **To ensure that patients will not receive ineffective treatments after sufficient evidence, two efficacy futility early stopping rules** will be implemented.

- The first futility early stopping rule will be applied after treating 14 patients with the tri-therapy at the RP2D level. If none of the 14 patients has 6-month response (CR or PR), the patient enrollment will be halted and the trial can be stopped for futility. This futility early stopping rule coincides with the first stage of the Gehan's design targeting 20% response rate with 95% confidence (26).
- The second futility early stopping rule will be evaluated every 10 patients after 20 patients are treated at the RP2D by applying the predictive probability (27). The trial can be stopped early if we see the following 6-month responses or less: 2 in 20, 3 in 30, 5 in 40, 6 in 50, 7 in 60, 9 in 70, 11 in 80, or 12 in 90 patients. The design has 5% type I error rate and 95% power with a null response rate of 10% and a target response rate of 30% at 6 months in the whole group. The probability of early stopping is 0.95, 0.31, and 0.04 if the response rate in the whole group is 10%, 20%, and 30%, respectively.

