#### **7.6. FINAL ANALYSIS**

It is expected that 130 patients will be enrolled over an 18-month period (phase 1, 6 to 8 months – phase 2, 8-12 months). With an additional 12/24 months of follow up, the total study duration will be 3 to 4 years. Final analysis will be performed after enrollment, treatment, and follow-up of all patients enrolled in the study. Both intent-to-treat and per-treatment analyses will be performed. Due to the nature of the Phase 2 study, no multiplicity adjustment will be made. All study findings will need to be validated by future studies.

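### The futility looks are timed by patients treated but count 6-month responses, so at the planned accrual they spare far fewer patients than the stated stopping probabilities suggest

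*Combined protocol and SAP*

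**What the plan says.** Section 7.2.1 sets two futility rules, and section 1.4 repeats them.

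- **First rule:** "The first futility early stopping rule will be applied after treating 14 patients with the tri-therapy at the RP2D level". Enrolment is halted if none of the 14 has a 6-month response.
- **Second rule:** "The second futility early stopping rule will be evaluated every 10 patients after 20 patients are treated at the RP2D". The boundaries are "2 in 20, 3 in 30, 5 in 40, 6 in 50, 7 in 60, 9 in 70, 11 in 80, or 12 in 90" responses or fewer.
- **Endpoint:** under the criteria of success in section 3.1, the 6-month response rate is the percentage "of patients achieving RECIST 1.1 complete or partial response within 6 months of treatment start".
- **Purpose:** section 1.2.1 says the rules are there "to guard against patients being enrolled in ineffective treatment".
- **Size and pace:** section 7.2 says "we expect to enroll approximately 120 patients in order to obtain 100 patients eligible for the study treatment". Section 7.6 says "It is expected that 130 patients will be enrolled over an 18-month period" and gives "phase 2, 8-12 months".
- **Stated performance (7.2.1):** the probability of early stopping is 0.95, 0.31 and 0.04 at true response rates of 10%, 20% and 30%.

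No section gives a minimum follow-up for a look, an accrual pause while outcomes are awaited, or a rule for patients treated for less than 6 months. Section 7.5 says monitoring runs throughout the first 100 patients.

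**The concern.** The trigger and the counted event run on different clocks. A look is due when the nth patient has been treated, but the nth patient's response status may not be known for up to 6 months. Phase 2 is planned to take only 8 to 12 months, so much of the cohort can be treated during that wait.

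The stated stopping probabilities are correct for responses known at once. They do not give the number of patients kept off an ineffective treatment, which is what the rules are for. An ethics committee or data monitoring committee reading 0.95 could take it as the chance that enrolment is cut short if the regimen is inactive. With pending patients undefined, two statisticians could also read the same look at different times and on different denominators.

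**Working it through.** **Inputs.** Looks and boundaries: 7.2.1. Lag: 6 months (section 3.1). Treated in the first part of phase 2: 100 (7.2). Phase 2 accrual: 8–12 months (7.6). Scans about every 8 weeks, the third at the end of cycle 6, which is week 24 or 168/30.44 = 5.52 months (Appendix 5). Uniform accrual is an assumption, because the documents give no accrual curve.

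**1. Reproduce the plan's figures.** I carried the exact binomial distribution of responses from look to look, removing paths at or below each boundary.

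| True rate | Stated | Looks 20–90 only | With the 0/14 look |
|---|---|---|---|
| 10% | 0.95 | 0.954 | 0.955 |
| 20% | 0.31 | 0.312 | 0.315 |
| 30% | 0.04 | 0.041 | 0.043 |

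The stated 95% confidence of the 14-patient rule also holds: 1 − 0.8^14 = 0.956. If success means at least 13 responses in 100 (the final cut-off is not stated), type I error is about 0.045 and power about 0.957–0.959, against the stated 5% and 95%.

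At a 10% rate the stopping probabilities by look are 0.229 (14), 0.452 (20), 0.065 (30), 0.105 (40), 0.023 (50), 0.014 (60), 0.033 (70), 0.027 (80) and 0.007 (90), with 0.045 for never stopping. Weighting each look by its n, and 100 for never stopping, gives a mean of 30.0 patients if responses are known at once.

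**2. Patients treated when a look is complete.** Treated = min(100, n + lag × 100/months of accrual). With a 6-month lag the added term is 50 (12 months), 60 (10 months) or 75 (8 months). With the week-24 scan it is 46, 55 or 69.

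| Look | 12 mo | 10 mo | 8 mo | 12 mo, wk 24 | 10 mo, wk 24 | 8 mo, wk 24 |
|---|---|---|---|---|---|---|
| 14 | 64 | 74 | 89 | 60 | 69 | 83 |
| 20 | 70 | 80 | 95 | 66 | 75 | 89 |
| 30 | 80 | 90 | 100 | 76 | 85 | 99 |
| 40 | 90 | 100 | 100 | 86 | 95 | 100 |
| 50 | 100 | 100 | 100 | 96 | 100 | 100 |
| 60–90 | 100 | 100 | 100 | 100 | 100 | 100 |

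The 10-month column matters. Section 7.6 gives 18 months in total and 6–8 months for phase 1, which leaves 10–12 months for phase 2, although the same sentence prints 8–12.

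**3. Probability of stopping while enrolment is open, true rate 10%.** Add the stopping probabilities of looks that complete before the 100th patient is treated.

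- 12 months: 0.229 + 0.452 + 0.065 + 0.105 = 0.851
- 10 months: 0.229 + 0.452 + 0.065 = 0.746
- 8 months: 0.229 + 0.452 = 0.681
- Week-24 scan: 0.874, 0.851 and 0.746 respectively

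**4. Mean treated, true rate 10%.** Replace n by the table values. For 12 months: 64 × 0.229 + 70 × 0.452 + 80 × 0.065 + 90 × 0.105 + 100 × 0.149 ≈ 75.9. The same sum gives 84.4 at 10 months and 95.2 at 8 months. With the week-24 scan the means are 72.4, 80.3 and 91.1.

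**5. Phase 1 patients at the RP2D.** These count in the looks (section 3.3.1). Assuming six of them, with 94 more treated over 8–12 months, the first two looks fall at 61 (14 + 6 × 94/12) to about 91 (20 + 6 × 94/8). The 50-patient look falls at 97 with 12-month accrual. The change is small, because the overrun is what accrues after the nth patient.

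**The case against.** Four points on the other side have weight.

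- **The upper figures rest on an 8-month phase 2.** That fits poorly with the 18-month total. At 10–12 months the first two looks fall at 64–74 and 70–80, and the mean treated is 76–84. This stands as a qualification; even so, most of the cohort is treated before the first look can be read.
- **Not everyone needs a full 6 months.** A response counts when seen, an early progressor is already a non-responder, and the week-24 scan is the last scheduled one in the window. A slow start across centres would also lower the early numbers. The numbers treated are therefore upper estimates. The plan does not, however, say that early-settled outcomes may be used.
- **Some protection remains.** At 12 months about 24 patients (100 − 76) are spared on average at a 10% rate. Later looks can still inform whether to add the optional second 100 patients. A reader might infer that the rules protect nobody; the figures do not support that.
- **The trigger need not be read literally.** The 20th patient is treated at month 1.6–2.4 (20/12.5 to 20/8.33), about when the first 8-week scans begin. A reader might infer that the 2-in-20 rule would then fire whatever the drug does and stop an active regimen. That reading is strained. The rule asks who has a 6-month response, which presupposes that 6-month status is known, and 7.2.1 says the trial can be stopped, not that it must be (1.4 says it will be). The point does not rest on that reading.

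**Conclusion.** The point holds as one about timing and disclosure. The boundaries and error rates are correct. What does not carry over is the step from the 0.95 early-stopping probability to patients kept off an ineffective treatment.

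At a true 10% rate with the planned 8–12 month accrual, the mean treated is about 76–95 where the boundaries imply 30. The chance of stopping with enrolment open is about 0.68–0.85. With the week-24 scan the ranges are 72–91 and 0.75–0.87. Looks from about 50 (12-month accrual), 40 (10-month) or 30 (8-month) onward can prevent few or no enrolments in the first 100.

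These figures assume uniform accrual, no pause, and looks read when every counted patient has completed the window.

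**What to change.** In sections 1.4 and 7.2.1:

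1. Define each look on the first 14, 20, 30 and so on RP2D patients, in order of treatment start, whose 6-month status is settled. Settled means CR or PR recorded; progression, death or off study without response; or 6 months elapsed. Keeping treatment order prevents a look from being filled with patients whose outcomes happen to settle early.
2. Count pending patients as neither responders nor non-responders.
3. Act as soon as the boundary is certain to be met. For example, 18 settled non-responders among the first 20 leave at most 2 responses.
4. State, under the planned accrual, the expected number treated at each look and the probability of stopping before enrolment closes. Say that looks completed after enrolment closes inform only the extension decision.

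The boundaries, sample size and accrual are unchanged, and no pause is needed. The cost is wording, a running tally of settled outcomes, and a less favourable stated protection.

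This recovers only some of the overrun. A simulation of the rule at a true 10% rate assumed exponential PFS with a median of 2–6 months (not in the documents), progression found at the next 8-week scan, and outcomes final at week 24. Mean treated was about 68–71 (12-month accrual), 76–79 (10-month) and 87–90 (8-month), compared with 72, 80 and 91 if every patient waits to week 24.

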### 7.2.2. Statistical analysis of the secondary efficacy end point and other endpoints

In addition to analyze response rate (RR), and PFS, we will measure other efficacy endpoints including best overall response rate, and overall survival (OS), etc. Kaplan-Meier estimate and Cox proportional hazards model will be applied to analyze time-to-event data such as PFS and OS. Our goal is to achieve OS  $\geq 60\%$  at 1.5 years for the matched patients.

## 7.3. SAFETY AND TOXICITY EVALUATIONS

The toxicity profile of each patient and each treatment regimen will be documented using the NCI CTCAE version 4.03. Severe adverse events will be reported to the study IRB and regulatory agencies. To ensure the safety of study patients, we will also implement the Bayesian toxicity

monitoring to alert the study investigators when the probability of unacceptable toxicity (DLT rate  $\geq$  33%) is higher than 50%. The corresponding toxicity stopping boundaries is to stop the trial if we see DLT in number of patients as follows: at least 4 in 10, 7 in 20, 10 in 30, 14 in 40, 17 in 50, 20 in 60, 24 in 70, 27 in 80, and 30 in 90 patients.

#### **7.4. STATISTICAL ANALYSES OF THE SECONDARY OBJECTIVES**

Descriptive statistics will be generated, standard statistical methods will be applied, and exploratory data analysis will be performed to achieve the goals for the secondary objectives. For example, the success rate of biopsy acquisition and the frequency and severity of biopsy related adverse incidence will be recorded and analyzed. The frequency and distribution of genomic/transcriptomic aberrations including DNA mutations/amplifications, RNA gene expression, and microRNA profiling in NSCLC will be estimated and analyzed. In addition, we will fine tune the SIMS algorithm using cumulative data and updated knowledge with the goal of enhance the overall performance of the predictive method. For example, available data both inside and outside the trial will be acquired to correlate genomic scores with treatments and the efficacy outcomes to improve the predictive algorithm. The institution variation will be estimated and efforts will be made to reduce the institution-to-institution variation.

#### **7.5. INTERIM ANALYSIS**

As described earlier toxicity and efficacy monitoring will be conducted throughout the first 100 patients. A descriptive interim analysis will be performed for this study after enrollment, treatment, and follow up of the first 50 patients, during which enrollment will continue. The PFS ratio will be estimated in all groups. No hypothesis testing will be performed and no early stopping rules will be implemented. The sample size re-estimation may be carried out should the observed improvements rates be much different from the estimated rates. This analysis will be share with FDA CDER in order to assess whether SIMS will be used prospectively or retrospectively in the second part of the phase 2 (=100) and if applicable there is need for an IDE application.

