## LIST OF ABBREVIATIONS

ADL	Activities of daily living
ADR	Adverse drug reaction
AE	Adverse event
ALP	Alkaline phosphatase
ALT	Alanine aminotransferase
AST	Aspartate aminotransferase
ANC	Absolute neutrophil count
CBC	Complete blood count
CDER	Center for drug evaluation and research
CDK	Cyclin-dependent kinases
CMC	Clinical monitoring committee
CMP	Complete metabolic profile
CNS	Central Nervous System
CR	Complete response
CRF	Case report form
CT	Computed tomography
CTCAE	Common Terminology Criteria for Adverse Events
DILI	Drug-induced liver injury
DLT	Dose limiting toxicity
DNA	Ribonucleic acid
DSMB	Independent safety and data monitoring committee
ECG	Electrocardiogram
EGFR	Endothelial growth factor receptor
EMA	European medicines agency
FFPE	Formalin-fixed paraffin-embedded
GDPR	General Data Protection Regulation
HAV	Hepatitis A virus
HBV	Hepatitis B virus
HCV	Hepatitis C virus
HIPAA	Health Insurance Portability and Accountability Act
HIV	Human immunodeficiency virus
ICF	Informed Consent Form
IDE	Investigational device exemption
IEC	Institutional ethics committee
IRB	Institutional review board
irAE	Immune-related adverse event
IV	Intravenous
LD	Longest diameter
MRI	Magnetic resonance imagery

MTD	Maximal tolerated dose
NCI	National Cancer Institute
NSCLC	Non-small cell lung cancer
OS	Overall survival
PCR	Polymerase chain reaction
PD	Progressive disease
PET	Positron emission tomography
PFS	Progression-free survival
PFS1	Progression-free survival on the immediate line prior SPRING
PFS2	Progression-free survival on the matched or unmatched SPRING therapy
PK	Pharmacokinetics
PR	Partial response
PS	Performance status
RECIST	Response Evaluation Criteria in Solid Tumors
RNA	Ribonucleic acid
RP2D	Recommended Phase 2 Dose
RPLS	Reversible posterior leukoencephalopathy syndrome
RR	Response Rate
SAE	Serious Adverse Event
SD	Stable disease
SIMS	Simplified interventional mapping system
SOP	Standard operating procedure
SPRING	Survival Prolongation by Rationale Innovative Genomics
SUSAR	Suspected unexpected serious adverse reaction

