### 1.4. SPRING STUDY SCHEMA

Refer to [Figure 2](#) below.

The trial design is a two-part, multiple parallel cohort, dose-finding and activity-estimating study. The study will enroll patients with metastatic NSCLC that have no targetable alterations (EGFR mutations or ALK translocation) and for whom targeted therapies are not recommended. In the first Phase 1 portion of the trial, patients may have received a maximum of two prior therapies for

metastatic NSCLC but in the second portion of the trial, ONLY patients who have not received prior systemic therapy in the metastatic setting will be included. All patients included must be ECOG 0-1. All patients must consent to a dual biopsy of the tumor tissue obtained from a metastatic lesion under radiologic guidance or from the primary tumor, and of normal matched tissue (bronchial mucosa), obtained through bronchoscopy under video guidance. The paired biopsy samples will be processed in a centralized facility for comprehensive analyses including genome sequencing and transcriptomics (mRNA and miRNA).

The primary objectives of the Phase 1 portion of the trial will be to establish the safety, tolerability, dose-limiting toxicities (DLTs), maximum tolerated doses (MTDs), and RP2Ds of the three drugs, administered concurrently, through enrollment in sequential dose-escalating.

**Figure 2:** Study design and planned retrospective analysis of the clinical utility of the SIMS algorithm and integrated genomic/transcriptomic analysis.

The statistical design of the trial has been performed by [name], University of Texas MD Anderson Cancer Center, Adjunct Professor of Statistics, Associate Vice Provost, Adjunct Professor of Biostatistics, Professor of Biostatistics, Biostatistics, Regular Member of the Graduate Faculty.

We estimate that we will treat up to 100 patients in the first part of phase 2 with futility early stopping rules.

For the first cohort of 100 patients it is expected that half of the patients will be PD-L1 positive and half of the patients will be PD-L1 negative. The hypothesized 6-month response rate in Arm A (fully matched) is 50%; in Arms B1, B2, and C1 (partially matched with two targets) is 40%; in Arm B3 (matched with PD-L1 only) is 30%; in Arms C2 and C3 (partially matched with VEGFR or CDK4/6) is 20%; and in Arm C4 (non-matched group) is 10%. The expected 6-month response rate is 30% in the entire group assume the triple therapy works.

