## 2.5. PREVIOUS EXPERIENCE - WINTHER STUDY

The study workflow and the use of dual biopsies were previously investigated in the WINTHER trial (<http://clinicaltrials.gov/show/NCT01856296>) of the Worldwide Innovative Networking (WIN) Consortium ([www.winconsortium.org](http://www.winconsortium.org)) for personalized cancer therapy (PI: [name]; Co-PI: [name]). WINTHER was built as a molecularly driven navigation trial. It was developed on the shoulders of previous trials:

- (i) The biomarker-driven trial pioneered by [name], which was one of the first to show that using biomarkers was feasible, and that, by using patients as their own controls (looking at PFS2 on matched therapy versus prior PFS), improved outcomes could be demonstrated without randomization (16).
- (ii) BATTLE study (17), which proved definitively that molecular profiling on fresh biopsies in lung cancer was feasible and safe.
- (iii) PREDICT, a navigation trial that showed that molecular matching (albeit non-randomized) was associated with substantially increased response rates PFS, OS, and PFS2/PFS1 ratio, even in the Phase I setting (18).
- (iv) NCI-Match, which started in 2015 and uses a similar molecularly driven, non-randomized strategy (19, 20).
- (v) Lung-Map in USA and CR-UK Matrix Lung in UK.

To date, the WINTHER study has been activated in 6 cancer centers (Gustave Roussy, Centre Léon Bérard, Chaim Sheba Medical Center, Val d'Hebron, MD Anderson Cancer Center and McGill Segal Cancer Center) across 5 countries (France, Spain, Israel, Canada, USA). The study has accrued

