#### **4.2. EXCLUSION CRITERIA**

***Note: Exclusion criteria should be verified between consent and registration (28 days maximum window).***

- Patients with documented oncogenic aberrations at enrollment: EGFR, ALK, ROS1 when available, MET exon 14 skipping when available. For squamous undifferentiated cell carcinoma, documentation of these aberrations is not mandatory.

Note: For Phase 1 portion, all patients with adenocarcinoma histology must have documentation of results for druggable oncogenic aberrations (EGFR mutations, ALK rearrangements, and ROS1 when available) prior to enrollment on the study.

- For Phase 1 portion, >2 lines of prior therapy in the metastatic setting.
- For the dose escalation phase of the study or until the MTD for the combination regimen has been determined, patients with moderate hepatic impairment defined as AST, ALT, ALP >5 times ULN, which would be grade 3 or higher. However, patients with liver metastases with AST/ALT ≤ 5 x ULN can be included in the study.
- For Phase 2 portion, any prior therapy in the metastatic setting.

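### The 50-patient interim plans an undefined PFS ratio in all groups, but phase 2 patients have no prior metastatic line from which PFS1 could be taken

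*Combined protocol and SAP*

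**What the plan says.** Section 7.5 sets the interim: "A descriptive interim analysis will be performed for this study after enrollment, treatment, and follow up of the first 50 patients". It is to involve no hypothesis test and no stopping rule. The one efficacy output it names is this: "The PFS ratio will be estimated in all groups". On use, it adds: "This analysis will be share with FDA CDER in order to assess whether SIMS will be used prospectively or retrospectively" in the second part of phase 2. It also allows the sample size to be re-estimated.

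The ratio is not defined in section 7 or in section 5.8. The list of abbreviations gives PFS1 as "Progression-free survival on the immediate line prior SPRING" and PFS2 as "Progression-free survival on the matched or unmatched SPRING therapy". The only place where a PFS ratio is described is the background in section 2.5, where an earlier molecular-matching trial "was associated with substantially increased response rates PFS, OS, and PFS2/PFS1 ratio, even in the Phase I setting".

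On prior therapy, the schema in section 1.4 says that for phase 2 "ONLY patients who have not received prior systemic therapy in the metastatic setting will be included". The exclusion list in section 4.2 reads "For Phase 2 portion, any prior therapy in the metastatic setting". Section 3.3.2 is stricter and allows no earlier treatment line. Phase 1 allows up to two prior lines, and phase 1 patients who receive the RP2D join the phase 2 efficacy assessment (sections 3.3.1 and 7).

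**The concern.** PFS2/PFS1 uses each patient as his or her own control. It needs a prior line with a recorded progression time. Phase 2 is a first-line study in the metastatic setting, so the denominator is missing for the population that the interim is meant to describe. The sentence looks suited to a trial in pretreated patients.

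At stake is what the sponsor shows at the 50-patient point. Section 1.4 says that a meeting with the FDA after data on about 50 patients will consider whether the second cohort repeats the design or enrols only SIMS-selected subgroups. If the only efficacy measure named for that analysis is blank for most patients, or comes from a handful of pretreated phase 1 patients, the by-group results will have to be chosen after the data are seen.

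**Working it through.** The plan states no sample size, precision or expected value for the PFS ratio, so there is no figure to reproduce. The check is who could have a ratio, and whether they could fill the groups.

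**1. Phase 2 patients.** Sections 1.4 and 4.2 exclude prior therapy in the metastatic setting; section 3.3.2 excludes any prior line. Metastatic-line PFS1 available: 0. Section 5.8 defines PFS only from the start of study treatment, and the flowchart in Appendix 5 has no item for PFS on earlier therapy.

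**2. Phase 1 patients at the RP2D.** Section 3.3.1 treats 3 patients at a level, expands to 6 under the DLT rule, and allows up to 3 more: 3, 6 or 6 + 3 = 9. Sections 3.3.1 and 4.2 set only a maximum of two prior lines (section 1.1 says one to two), so some may be untreated and the floor is 0. Let m be the number with a prior line among the first 50 at the RP2D. Then m is about 0 to 9, and 50 − 9 = 41 to 50 of the 50 (82% to 100%) have no ratio. Intra-patient escalation to the RP2D could add a few contributors.

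**3. Widest reading of the first 50.** If the interim counts all phase 1 patients (about 30 treated, section 1.2.1), at most 30 of 50 (60%) could contribute, and 20 of 50 (40%) still could not.

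**4. Filling the groups.** Planned shares from section 7, per 100 patients: A 10, B1 13, B2 12, B3 15, C1 11, C2 8, C3 16, C4 15. Assume contributors fall into the arms independently with these shares.

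- Expected number in Arm A = 0.10 × m.
- Chance that Arm A is empty = (1 − 0.10)^m.
- Chance that all eight arms have at least one: 0 for m below 8. For m = 9, exactly one arm holds two patients, so the chance is (9!/2) × (product of the eight shares) × (sum of the shares) = 181,440 × 4.942 × 10⁻⁸ × 1 = 0.0090. For m = 30, inclusion-exclusion gives 0.799.

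| m | Share of 50 | Expected in Arm A | Arm A empty | All eight arms represented |
|---|---|---|---|---|
| 0 | 0% | 0 | 100% | 0 |
| 3 | 6% | 0.3 | 73% | 0 |
| 6 | 12% | 0.6 | 53% | 0 |
| 9 | 18% | 0.9 | 39% | 0.9% |
| 30 (all phase 1) | 60% | 3.0 | 4% | 80% |

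In the last row the arms would probably not be empty, but each would hold about 2.4 (C2) to 4.8 (C3) patients on average. All would be from phase 1 and treated across several dose levels, so they would not describe the first-line RP2D population.

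**The case against.** The strongest case on the other side has four parts.

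- **The consequence is limited.** A reader might infer that the FDA decision on SIMS would rest on a quantity that cannot be computed. The documents do not say so. What is shared is the whole descriptive interim, and nothing makes the PFS ratio the criterion. Re-estimation is tied to observed against estimated rates, and the only group-level rates that section 7 estimates are 6-month response rates. This objection stands.
- **Useful analyses already exist.** Section 7.2.1 has a whole-group response look at 50 patients and a posterior-probability search for response signals in predefined SIMS subgroups. Section 7.2.2 plans Kaplan-Meier and Cox analyses of PFS. The trial would not be without SIMS-by-outcome information. This stands too, although 7.5 does not refer to these as interim outputs.
- **Prior non-metastatic therapy.** A reader might infer that PFS1 is undefined for every phase 2 patient without exception. Sections 1.4 and 4.2 bar only metastatic-setting therapy, and the PFS1 definition is not limited to metastatic lines. A patient with earlier adjuvant or locally advanced treatment might have some PFS1. Section 3.3.2 points the other way, and no section plans to collect it. The safe statement is that there is no metastatic-line PFS1.
- **The ratio might mean something else.** A between-group PFS ratio is conceivable, since the planned contrasts are across arms. No reference group or definition is given, and the PFS1 and PFS2 entries point to PFS2/PFS1. If a between-group ratio was meant, 7.5 still needs to say so.

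**Conclusion.** The point holds as a mismatch between a planned interim output and the eligibility criteria. On the only definition the documents support, the PFS ratio cannot be estimated in the phase 2 population from any prior metastatic line. About 0 to 9 of the first 50 patients at the RP2D could have one, or at most about 30 of 50 if all phase 1 patients count. At the RP2D, coverage of all eight SIMS arms is effectively out of reach.

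These counts are assumptions drawn from the escalation rules. The arm probabilities further assume that the planned shares apply to pretreated phase 1 patients and that every contributor has a SIMS result; failed biopsies would lower the numbers.

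The effect is moderate. The interim has no test or stopping rule, and the primary endpoint, 6-month response, is untouched. It should be corrected because it is the only efficacy measure that 7.5 names for an analysis going to the regulator, and the correction is easy.

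**What to change.** Delete the PFS ratio sentence from section 7.5. In its place, state that for the first 50 patients the interim will report the 6-month response rate with exact confidence intervals and Kaplan-Meier PFS, by number of SIMS-matched targets (three, two, one, none). This agrees with sections 7.2.1 and 7.2.2. With the planned shares of 10%, 36%, 39% and 15%, 50 patients give about 5, 18, 19.5 and 7.5 per group, so every group is expected to have patients, although the fully matched group will be small. State also whether the first 50 means patients treated at the RP2D or all patients in the study.

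If the sponsor wants to keep the ratio, define it as PFS2/PFS1, restrict it to phase 1 patients with a prior line, and report it separately from the first-line results.

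Replacing the sentence is a small edit to 7.5 with no new data: response and PFS are already collected, and section 7 expects SIMS scores within three months of treatment start. Keeping the ratio would also require recording prior-line PFS for the phase 1 patients concerned.
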